### **9.4.3. Operational Exposure Definition**

When a pregnant woman enrolls in the study, she will be asked when she was last treated with galcanezumab. When a pregnant woman is enrolled by her HCP, the HCP will provide this information. The pregnant woman will then be asked to provide a medical release that allows the RCC to confirm galcanezumab treatment with the appropriate source. Reported galcanezumab injection at any time during pregnancy (from four months prior to LMP until pregnancy outcome) will constitute a fetal exposure. Galcanezumab exposure will be further categorized by earliest trimester of exposure.

For this study, gestational weeks will be estimated from the most reliable EDD as reported by the HCP or the pregnant woman. If a CEDD is provided by the HCP, it will be used instead. The date of conception will be calculated as the most reliable EDD minus 38 weeks. If the EDD is not available or never estimated, the first day of the LMP may be used to estimate gestational age. The second trimester will be considered to begin at week 14 after LMP, and the third trimester at week 28. If there is a discrepancy between gestational age calculated from LMP and reported gestational age, the HCP will be asked to verify the data.

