## PPD

Embryo-fetal development studies conducted in rats and rabbits at exposures up to 29 times the highest proposed clinical dose of 300 mg revealed no evidence of harm to the developing fetus and there were no effects on survival, growth, sexual maturation, behavior, or reproduction in offspring exposed to galcanezumab in utero and through lactation at exposures up to 16 times the highest proposed clinical dose of 300 mg in the prenatal and postnatal development study in rats.

The current nonclinical data and the low number of pregnancy outcomes in humans are insufficient to draw conclusions about the effect or safety of galcanezumab exposure during human pregnancy. However, migraine prevalence is highest in women aged 18 to 49 years (Buse et al. 2012) during typical childbearing years. There is often a medical need for preventive treatment of migraine during pregnancy, with treatment decisions based on clinical judgement of the benefits and the potential harms (Cassina et al. 2010). It is anticipated that given the treated patient population and the long half-life of galcanezumab, exposure during pregnancy will occur in the post-authorization setting and thus, further study is warranted.

Reviews of studies evaluating pregnancy outcome in women with migraine generally conclude that migraine, treated or untreated, probably has no effect on most pregnancy outcomes, including risk of congenital anomalies (MacGregor 2012; Menon and Bushnell 2008). Women with migraine have been reported to be at increased risk of developing hypertensive disorders such as pre-eclampsia in pregnancy compared to women without migraine (Banhidly et al. 2007; Facchinetti et al. 2009) which is associated with an increased risk of low birth weight (preterm birth, small for gestational age infant) (Adeney et al. 2005, Simbar et al. 2010, Facchinetti et al. 2009). In the migraine population, more severe migraine, defined by greater frequency and intensity, is associated with increased prevalence of cardiovascular comorbidity and comorbid affective disorders such as anxiety and depression (Chen et al. 2012; Goulart et al. 2014).

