## 8. Research Question and Objectives

The purpose of the study is to prospectively evaluate pregnancy, maternal and infant outcomes through 12 months of age among women exposed to galcanezumab during pregnancy, as well as in two galcanezumab-unexposed comparison groups.

The primary objective is to describe the occurrence of congenital malformations (main outcome), pregnancy outcomes, maternal pregnancy complications, infant outcomes at birth and infant events of interest up to 1 year post-delivery among women exposed to galcanezumab, as well as in 1) women with migraine not exposed to CGRP antagonists and 2) women without migraine:

- Congenital malformations (major and minor)
- Pregnancy outcomes (recognized spontaneous abortions, molar pregnancy, ectopic pregnancy, elective terminations, stillbirths)
- Maternal pregnancy complications (pre-eclampsia, hypertension)
- Infant outcomes (preterm birth and small-for-gestational-age births)
- Infant events of interest (postnatal growth and development up to one year of age)

The secondary objective is to estimate, where statistically feasible, the relative occurrence of congenital malformations, pregnancy, maternal, and infant outcomes among women exposed to galcanezumab as compared to 1) women with migraine not exposed to CGRP antagonists and 2) women without migraine.

Exploratory objective: Additional available published external comparator data sources in women with migraine and the general population for estimates of selected outcomes will be evaluated to contextualize observed outcome occurrences in the registry.

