### **9.3. Variables**

#### **9.3.1. Exposure of Interest**

The exposure of interest is treatment with galcanezumab at any time during pregnancy or up to 4 months prior to conception. Any injection of galcanezumab within 4 months prior to the LMP is considered exposed due to its long half-life. Data will be collected regarding dates of treatment and number of doses. The trimester of exposure will also be captured.

CGRP antagonist-unexposed women with migraine will not have been treated with CGRP antagonists at any time during pregnancy or up to 4 months prior to conception, but may have been treated with other prescribed or over-the-counter migraine therapies.

Treatment is not under control of the study but administered solely at the discretion of the pregnant woman's treating HCP and as part of routine clinical care. Only data that are routinely recorded in the course of usual care among women treated with galcanezumab during pregnancy will be collected.

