**Table 1. Summary of patient follow-up and data collection timepoints**

Information Requested	Maternal Contact (Patient)		Maternal HCP Contact			Infant HCP Contact		Evaluator
	Enrollment	Outcome e	Registration	Interim Follow-Up (2 nd trimester)	Outcome Follow-Up	Follow-Up (at birth) f	Follow-Up (4 and 12 months)	Targeted Follow-Up
Reporter Information and Permissions								
Report source, permission to contact HCP (for pregnant patient), pediatrician, and alternate patient contact information as applicable	✓	✓ e	✓					
Maternal Information								
Maternal characteristics (age, ethnicity, disease status)	✓		✓					
Maternal prenatal information (LMP, EDD, CEDD, prenatal test results & timing)	✓		✓	✓ a	✓ a			
Obstetrical history (maternal and paternal)	✓		✓					✓ d
Family history (maternal and paternal)	✓		✓					
Galcanezumab therapy (indication for use, dates of administration) (maternal/paternal as appropriate)	✓ g		✓	✓ a, g	✓ a, g			
Concomitant medications (Rx, OTC, dietary supplements, herbals), during pregnancy (dosage, routes, start/stop date of administration), recreational/illicit drug, alcohol and tobacco use during pregnancy	✓		✓	✓ a	✓ a			
Maternal concurrent medical conditions	✓		✓	✓ a	✓ a			

Outcome of Pregnancy Information								
Pregnancy status	✓		✓	✓	✓ a			
Outcome information (fetal loss, live birth, gestational age, weight)				✓ b	✓	✓ f		
Birth defect noted, description, attribution, if applicable				✓ b	✓			
Other factors that may have contributed to outcome (etiology)				✓ b	✓			✓ d
Infant Follow-up Information								
Birth defect noted, description, attribution, if applicable						✓ cf	✓ ac	
Other factors that may have contributed to outcome (etiology)						✓ cf	✓ ac	✓ d
Developmental delays noted						✓ f	✓ ac	

a Obtain updated information since the previous contact.

b Obtain this information if outcome has occurred.

c Collect only for live birth outcomes.

d Collect information not previously obtained, to facilitate the characterization of the fetal loss and/or birth defect(s).

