#### **9.4.1.3. Information Collected at Pediatric Follow-up**

##### *Timing of Pediatric Follow-Up*

If a live birth occurs, the mother is asked to give consent for the infant's pediatrician to provide follow-up information. If consent is obtained, the pediatrician completes the *Pediatric Follow-Up Form* at 4 and 12 months of age.

Pediatric Follow-up FormInfant Outcome

- Date of follow-up evaluation
- Current age of infant
- Current weight of infant
- Developmental milestones per the HCP's assessment of normal, delayed, etc.
- Congenital malformation(s) and details, if noted
- Type of congenital malformation(s) if applicable, attribution to galcanezumab drug therapy, and other factors that might have contributed to the outcome

Targeted Follow-up after report if an event of interest

If there is a congenital malformation, in order to properly characterize the event, additional information may be requested from the reporting HCP on the *Targeted Follow-up Form*:

- Details of the congenital malformation
- Etiology
- Maternal infections of relevance to congenital malformations
- Other information considered relevant by the HCP
- Specific questions requested by the congenital malformation evaluator

**9.4.2. Follow-up process**Attempts to Obtain the Follow-Up Information

In the month that the follow-up is due, the HCP will be contacted and asked to provide follow-up information. Three subsequent attempts, as necessary, will be made every two weeks via various modes of communication, e.g., phone, fax, email, mail. If the missing follow-up data is essential to characterize the outcome or event and there is still no response from the provider, a final communication will be sent indicating the case is lost to follow-up. If this communication prompts a response from the HCP or the requested data is later received, the case will be re-opened and assessed for evaluability. If, at any point in the follow-up process, the reporter specifically indicates that the patient is lost to follow-up, no further attempts will be made, but an attempt to obtain information on the cause of loss to follow-up will be made.

Follow-Up Process for Clarification of Information

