### 9.6.1. Data Processing

Data for this prospective observational safety study will be managed with an electronic data capture (EDC) platform, Cisiv Baseline Plus, which is 21 CFR Part 11 compliant. Only the variables described in the protocol under section 9.3 will be solicited and entered in the EDC. Participants and/or their HCPs will provide data over the phone or by completing a paper case report form (CRF), which can be submitted to the RCC via mail, email or fax. The data will be reviewed by a registry central monitoring associate (CMA) associate for correctness and completeness and entered into the database.

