### **9.7.2. Statistical Methods**

Overall and stratum-specific (e.g., timing of exposure to galcanezumab (prior to conception vs. during pregnancy, as well as trimester of exposure), maternal age group) point estimates and 2-sided 95% confidence intervals will be calculated using the exact binomial distribution for prevalence of congenital malformations among evaluable patients, preterm birth and SGA among evaluable patients with live births, preeclampsia and hypertension in pregnancy and infant growth and development through one year for each of the galcanezumab exposed, CGRP antagonist-unexposed migraine and general population, non-migraine groups.

If applicable, frequencies of the events of interest will be presented by pregnancy outcome.

Most structural defects have their origins in the first trimester of pregnancy, the period of organogenesis. In addition to overall prevalence of observed MCM, the analysis of MCMs will be stratified by trimester of earliest exposure to galcanezumab. The prevalence of combined MCMs reported to the study will be calculated as a proportion with the number of observed MCMs as the numerator and the number of live births as the denominator, among women with first trimester exposure. CDC MACDP uses these figures to calculate the prevalence, and in order to compare the observed study prevalence with the background prevalence, it is decided to use the same method. Pregnancy losses occurring at or after 20 weeks' gestation with reported MCMs will be included in the numerator of the estimate of prevalence for MCMs as a conservative approach. This method also allows comparison of outcomes with the CDC MACDP. The reason MACDP uses this method is because a slight overestimate is preferred to a potential underestimate. This is due to not taking into account stillbirths in the denominator (but counting the MCM's recognized in stillbirths in the numerator). However, given the very low prevalence of stillbirths as pregnancy outcomes in the general population, this is only a very small possible overestimate. The prevalence of observed MCMs in exposed cases will be compared with the most recent reported prevalence of the CDC MACDP. Additionally, if a sufficient sample size is attained for each trimester exposure group, it may be possible to compare the prevalence of MCMs among exposures to galcanezumab in the first trimester versus

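### One-year infant growth and development is estimated by cohort, but maternal treatment after delivery and infant feeding are not recorded, so in-utero and possible milk exposure cannot be told apart for this endpoint

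*Protocol*

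**What the plan says.** Section 8 makes the description of infant events part of the primary objective: "infant events of interest up to 1 year post-delivery among women exposed to galcanezumab", and likewise in the two comparison groups. Section 9.7.2 plans exact binomial estimates with 95% confidence intervals for "infant growth and development through one year for each of the galcanezumab exposed" and comparison groups. The data behind them are listed in Sections 9.3.2.7 and 9.4.1.3: evaluation date, infant age, weight, and "Developmental milestones per the HCP's assessment of normal, delayed, etc". They are reported by the infant's pediatrician at 4 and 12 months.

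Exposure runs over a different period. Section 9.3.1 states: "The exposure of interest is treatment with galcanezumab at any time during pregnancy or up to 4 months prior to conception". Section 9.4.3 gives the operational form: "Reported galcanezumab injection at any time during pregnancy (from four months prior to LMP until pregnancy outcome) will constitute a fetal exposure". The Table 1 row "Galcanezumab therapy (indication for use, dates of administration) (maternal/paternal as appropriate") is ticked at enrollment, registration, second-trimester and outcome contacts, and footnote g confines the self-reported and follow-up ticks to the exposed group. The concomitant-medication row and Section 9.4.1.1 both refer to use during pregnancy. Section 9.6.1 then closes the list: "Only the variables described in the protocol under section 9.3 will be solicited and entered in the EDC".

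**The concern.** The outcome window runs a year beyond the exposure window. Three kinds of exposed-cohort mother would be recorded identically: one who is treated after delivery and breastfeeds, one who is treated and does not breastfeed, and one who is not treated again. A migraine control who starts a CGRP antagonist after delivery would also go unseen.

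A cohort difference in 12-month weight or milestones could then reflect fetal exposure, continuing exposure through milk, or a difference in feeding. A reassuring result has the same problem, since it would pool infants with and without postnatal exposure in unknown proportions. The study question concerns exposure during pregnancy, and for this endpoint the data cannot isolate it.

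**Working it through.** The protocol states no figure on this point, so the check is mainly a comparison of sections.

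**1. Outcome window.** Birth to 12 months, with pediatric contacts at 4 and 12 months (Sections 8, 9.3.2.7, 9.4.1.3, 9.7.2).

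**2. Exposure window.** Four months before the last menstrual period to pregnancy outcome (Section 9.4.3). Section 9.3.1 has no postpartum period either.

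**3. Overlap in Table 1.** At the 4- and 12-month contacts the ticked rows are birth defects, other contributing factors and developmental delays. Neither the galcanezumab row nor the concomitant-medication row is ticked in any infant column. The mother herself has no scheduled contact after the one used to obtain the pediatric release.

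**4. Can Section 9.3 supply the missing items?** For treatment, partly: Section 9.3.3.7 lists medications, including migraine treatment, without an end date, so Section 9.3 does not rule out postpartum use. The limit to pregnancy comes from Table 1 and Section 9.4.1.1. For feeding, no: no part of Section 9.3, Table 1 or the form contents includes it, so Section 9.6.1 excludes it.

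**5. Could another field catch it?** The pediatric form asks about attribution to galcanezumab and other contributing factors, but Section 9.4.1.3 ties that item to malformations. Table 1 shows contributing factors as a separate row without that tie. In either reading it is unstructured and requires neither dosing dates nor feeding.

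**6. Do recorded pregnancy doses stand in for postnatal exposure?** Section 7 gives a half-life of 27 days. Assuming simple exponential elimination in the mother, the fraction remaining t days after her last dose is 0.5^(t/27):

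- t = 30: 0.5^(1.11) = 0.463
- t = 91: 0.5^(3.37) = 0.097
- t = 122 (about four months): 0.5^(4.52) = 0.044
- t = 365: 0.5^(13.52) = 0.0001

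Even after a dose close to delivery, about 4% would remain in the mother at four months. Dates that stop at delivery therefore say little about maternal drug between the 4- and 12-month visits. Any dose in that period is a separate source, and it is not recorded. The calculation concerns the mother only and says nothing about infant levels.

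**7. Is it acknowledged?** Section 9.9 discusses selection, prenatal testing, loss to follow-up, comparator treatments and migraine severity. It does not mention postpartum treatment or feeding.

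**The case against.** The strongest reply is that this is a pregnancy registry and lactation is not its question. Growth and development is mainly descriptive: the secondary, comparative objective in Section 8 names infant outcomes, which Section 8 defines as preterm birth and small for gestational age, and does not name infant events of interest. This stands and limits the point to one endpoint. It does not remove it, because Section 9.7.2 still produces estimates by cohort and Section 9.7 allows relative occurrence of the study outcomes where feasible. Readers will set those columns side by side.

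Three stronger readings are tempting, and the documents do not support them.

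- A reader might infer that the protocol itself treats lactation as a relevant human exposure route, since Section 7 mentions offspring "exposed to galcanezumab in utero and through lactation". That sentence reports a rat study that found no effects. It shows only that the cited nonclinical evidence combined the two periods.
- A reader might infer that Section 9.3 shuts out postpartum treatment altogether. Section 9.3.3.7 has no end date; only feeding is absent outright.
- A reader might want a count of affected infants, by applying an assumed resumption rate to the 350 to 400 live births in Section 9.5. The documents give no such rate. The result would count treated mothers rather than infants exposed through milk, and it would ignore that 12-month data need the mother's consent and the pediatrician's reply.

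A practical objection also stands. The 4- and 12-month contacts reach only the infant's provider, and Section 9.4 limits collection to routine-care data. The documents do not say whether a pediatric record would hold the mother's injection dates. The contact for the pediatric release falls at enrollment or around the expected delivery date, too early to learn about later treatment or feeding.

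**Conclusion.** The gap is real and narrow. Infant weight and development are estimated by cohort through one year, while treatment data stop at pregnancy outcome and feeding data are never gathered. For this endpoint the study cannot distinguish in-utero exposure from possible exposure through milk, or from feeding differences between cohorts. A later analysis plan cannot repair this.

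Malformations (the main outcome), pregnancy outcomes, preterm birth, small for gestational age and maternal complications are unaffected. The size and direction of any bias cannot be computed from the documents. The conclusion rests on the text of the collection schedule and not on any assumed rate of postpartum treatment or breastfeeding. It does presuppose that some mothers are treated after delivery or that feeding differs between cohorts; the documents neither state nor exclude this. It is an inexpensive improvement that makes one result interpretable, and not a flaw in the study's central aim.

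**What to change.** Add two items to Section 9.3, Table 1 and the existing 4- and 12-month Pediatric Follow-up Form, in all three cohorts:

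1. Infant feeding since the last contact: any breast milk (yes/no), with stop date.
2. Any known maternal CGRP antagonist use since delivery: yes/no/unknown, with dates if available.

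The second item must not inherit the exposed-group-only restriction of Table 1 footnote g.

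Report growth and development in exposed infants with and without possible lactation exposure, labelled as a descriptive or sensitivity analysis. Do not adjust for breastfeeding in the main cohort comparison: it arises after exposure and may itself be affected by treatment choice or migraine severity, so conditioning on it can introduce bias. State in Section 9.9 that fetal and postnatal exposure can be separated only as far as these items are answered.

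The cost is a slightly longer form and one additional table. Maternal treatment will be unknown for some infants where only the pediatrician replies. A brief maternal contact at 4 and 12 months would reduce that, but it would be a new contact with its own cost, and the sponsor should decide whether this endpoint warrants it. If neither item is added, the Section 9.9 statement is the minimum.

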### **9.4.4. Operational Outcome and Event Definition and Identification Process**

All pregnancy outcome and maternal/infant events of interest variables will be provided by the treating or obstetric HCP and the infant's pediatrician. In case no data on the pregnancy outcome can be obtained from the HCP, the pregnant woman will be asked to provide information on the pregnancy outcome. The HCP will be asked to describe any congenital malformations observed in the infant or fetus at birth and will also be asked to report the gestational age and birthweight, as described in the medical records. These last two variables will be used to calculate preterm birth (gestational age <37 weeks at birth) and SGA (birth weight  $\leq$ 10th percentile for gender and gestational age) in live births. A teratologist/geneticist will review all reported congenital malformations and classify them using the CDC's MACDP system as specified in 9.3.2.

This review includes identification of specific aspects of the case for further inquiry from the reporter(s), clarification and classification of the defect(s) reported (in accordance with the classification conventions of the MACDP (CDC, 1998) and a classification system, developed by Scheuerle (Scheuerle and Tilson, 2002) to increase the ability to generate potential signals. In addition, the review includes definition of the potential relevance of timing of exposure to the event(s) reported –'temporality assessment'.

The congenital malformation evaluator assessment includes the following:

- The evaluator may assess a report as "pending further information" if more information is needed to determine the etiology of the defect and/or the temporality. However, if no further information is received despite repeated attempts, the evaluator makes an assessment based upon available information.

The assessments of temporality with the Registry drug exposure are classified as one of the following:

- Pending
- The development of this defect and the timing of the exposure to drug cannot rule out a possible association
- No temporal association
- Unable to assess
- Defect with known cause, temporality may be irrelevant
- Pathogenesis of this defect has yet to be defined specifically enough to assess temporality
- Not a defect

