#### **9.4.6. Scientific Advisory Committee**

A Scientific Advisory Committee (SAC) will be established to oversee the scientific affairs of the study, including its ongoing monitoring. A charter for SAC activities, roles and responsibilities and meeting frequency will be established at study start. The SAC will comprise recognized experts including (but not limited to) the fields of teratology, epidemiology, maternal and fetal medicine, as well as migraine treatment. The SAC will meet regularly to review the accumulated body of data from the study, including review and classification of reported MCMs and other events of interest, and to carry out any actions required, including review and interpretation of interim data analyses and reports and publications of study data. The SAC may meet on ad hoc occasions if indicated. In addition to the above activities, the SAC might support in the design and implementation of strategies to heighten awareness of the study.

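### Malformation classification and the galcanezumab temporality assessment sit in one review, and no step keeps case classification apart from knowledge of cohort or exposure

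*Protocol*

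**What the plan says.** Section 9.4.4 names one assessor: "A teratologist/geneticist will review all reported congenital malformations and classify them using the CDC's MACDP system as specified in 9.3.2". The next paragraph lists what that review covers: points in the case to pursue with the reporter, "clarification and classification of the defect(s) reported", and, as an addition, temporality, in that "the review includes definition of the potential relevance of timing of exposure to the event(s) reported". The result scale is introduced with "The assessments of temporality with the Registry drug exposure are classified as one of the following". Seven classes follow, and *Not a defect* is the last.

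Other parts of the protocol bear on the same decision:

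- Section 9.4.1.3 lets the targeted follow-up form carry "Specific questions requested by the congenital malformation evaluator".
- Section 9.4.6 gives the SAC a role "including review and classification of reported MCMs and other events of interest", alongside its regular look at the accruing data.
- Section 9.3.2.2 sets the case definition. It follows MACDP, adds a rule that three or more conditional defects make a case, and has exclusions for prematurity-related findings and for transient, infectious or biochemical conditions.
- Section 9.7.2 admits to the primary analysis only reports classified as a major defect or as three or more minor ones.

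No section mentions masking the evaluator or the SAC. The only blinding language is in 11.2, on product complaints. The limitations in 9.9 do not raise the matter.

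**The concern.** Temporality against galcanezumab cannot be assessed without exposure dates, and it has meaning only for exposed pregnancies. When it shares a review with the decision on whether a finding is a malformation, the assessor may know the cohort while settling case status. Malformations are the main outcome. Their prevalence is described in three cohorts, and the secondary objective compares exposed women with two internal groups where that is feasible. Section 9.2.4.1 relies on the internal general-population group being directly comparable, which needs the same standard of case ascertainment in each cohort.

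If borderline reports are read more generously, or queried more closely, in one cohort, the prevalence in that cohort shifts for reasons unrelated to the drug. The direction cannot be predicted: an assessor alert to a signal may over-call exposed cases, and one who thinks the drug harmless may under-call them. A larger sample would not average this error away.

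**Working it through.** No figure in the protocol is in dispute. The check has two parts: what the text fixes, and how sensitive the outcome is.

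**Text, side by side**

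1. *Same review?* Yes. In 9.4.4 classification, points for query and temporality are all parts of the one review.
2. *Order or lock?* None is stated. Classification is described first and temporality second, but nothing requires the first to be recorded before exposure is seen.
3. *Masking?* None is stated for the evaluator (9.4.4) or the SAC (9.4.6).
4. *Room for judgement?* Some. Under 9.3.2.2 a transient, infectious or biochemical condition is set aside unless it might reflect a defect not yet recognised. A finding in an infant born before 36 weeks is set aside if prematurity explains it. The count rule for conditional defects is mechanical once the findings are known, but the findings can depend on what is asked.
5. *Does the decision matter?* Yes. Section 9.7.2 uses it to decide who is a case.

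**Sensitivity (the number of shifted reports is an assumption)**

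Inputs from section 9.5: baseline risk 2.78%; 420 evaluable exposed women; about 350 to 400 live births. Section 9.7.2 uses live births among first-trimester exposures as the MCM denominator, so 420 is too large a base and both are shown. I assume the same size and risk in the comparison cohort, and no true effect.

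Expected cases e = n × 0.0278. If k reports are classified differently in the exposed cohort only, the apparent ratio is (e ± k)/e.

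| n | e | k = +1 | +2 | +3 | −1 | −2 | −3 |
|---|---|---|---|---|---|---|---|
| 350 | 9.73 | 1.10 | 1.21 | 1.31 | 0.90 | 0.79 | 0.69 |
| 400 | 11.12 | 1.09 | 1.18 | 1.27 | 0.91 | 0.82 | 0.73 |
| 420 | 11.68 | 1.09 | 1.17 | 1.26 | 0.91 | 0.83 | 0.74 |

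Restricting to first-trimester exposure lowers e further, so each shifted report weighs more.

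**Against sampling error.** For a ratio of 1.00, the standard error of the log ratio is √[2(1/e − 1/n)].

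- n = 420: √[2(1/11.68 − 1/420)] = 0.408. The 95% interval is exp(±1.96 × 0.408) = 0.45 to 2.2.
- n = 350: √[2(1/9.73 − 1/350)] = 0.447. The interval is 0.42 to 2.4.

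Every ratio in the table lies inside these limits. To produce the twofold ratio that the study is sized for, about four reports would have to move up in the exposed cohort and four down in the comparator: (11.68 + 4)/(11.68 − 4) = 2.04.

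**The case against.** The strongest reply is that the protocol never says the evaluator is unmasked. Its wording is compatible with classifying first and assessing temporality afterwards, and the SAC charter, which is not shown, could add safeguards. This stands in part. A reader might infer that case status is set with exposure known, but the text supports only that nothing separates the two.

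Four further inferences are tempting, and the document does not carry them.

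- *That Not a defect proves the case decision is made on the temporality scale.* It may simply mark that temporality does not apply. Case status is governed by 9.3.2.2 and 9.7.2.
- *That the attribution field discloses the cohort.* Section 9.4.1.3 does name the drug, as "attribution to galcanezumab drug therapy, and other factors that might have contributed to the outcome". But 9.3.2.2 words the item generically, Table 1 does not mark it as exposed-only, and no passage says the evaluator receives it.
- *That the evaluator picks which cases are queried.* Section 9.4.4 lets the evaluator choose aspects of a case for inquiry, not which cases are followed up.
- *That a signal would be created or hidden.* The assumed shifts lie well within sampling error. The primary objective is descriptive, and comparison with the internal groups is secondary and conditional on feasibility.

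It is also fair that MACDP criteria narrow discretion and that masking cannot be complete, since a migraine history or migraine drugs can give the cohort away. These points limit the size of the problem. They do not supply the missing separation, and the charter governs the SAC, not the evaluator's procedure in 9.4.4.

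**Conclusion.** The point holds as a weakness in how the outcome review is arranged. Section 9.4.4 combines classification and exposure-timing assessment under one evaluator, and neither it nor 9.4.6 keeps case classification independent of cohort or exposure. The consequence is possible differential classification or querying of borderline reports. The direction is unknown, and both the descriptive prevalence and the secondary comparison with the two internal groups are affected.

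On the assumption of one to three affected reports in one cohort, with 10 to 12 expected, the ratio moves by roughly 10% to 30%. A shift of this kind would be systematic, although it is smaller than the sampling error. The document gives no rate of borderline reports, so this is an illustration and not an estimate. The case for change rests on the separation being cheap and the classification deciding the main outcome. There is no evidence that bias will occur.

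**What to change.** Rewrite the review in 9.4.4 as two steps by the same evaluator.

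**Step 1.** Classify every report from all three cohorts and raise queries on a narrative from which the RCC has removed cohort, galcanezumab dates, drug attribution and, as far as possible, migraine diagnosis and migraine medications. Record the classification, including *Not a defect*, before exposure is shown. Reports that are pending, or that gain information at 4 or 12 months, are re-classified on the same masked basis and the change is documented.

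**Step 2.** Reveal exposure and record etiology and temporality for exposed cases, without altering the step 1 case status.

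In 9.4.6, state that any SAC reclassification used in the analysis is made on a cohort-masked listing.

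**Cost.** Protocol wording and modest RCC redaction, repeated when new information arrives and covering minor and transient reports as well as major ones. Masking will be incomplete in some cases, and temporality will be recorded slightly later. No extra assessor or larger sample is needed. Reporting of serious adverse events is unaffected, because 11.1.1 counts from awareness of the event.
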